#### 8.1.2 Serious Adverse events

An SAE is any untoward medical occurrence that at any dose fulfills one or more of the following criteria:

- results in death,
- is immediately life-threatening,

*The term “life-threatening” in the definition of “serious” refers to an event in which the patient was at immediate risk of death at the time of the event; it does not refer to an event which hypothetically might have caused death if it were more severe.*

- results in persistent or significant disability/incapacity,

*Disability is defined as a substantial disruption in a person’s ability to conduct normal life functions (i.e. the AE resulted in a significant, persistent, or permanent change, impairment, damage, or disruption in the patient’s bodily function/structure, physical activities, or quality of life).*

- is a congenital anomaly/birth defect,
- requires inpatient hospitalization or prolongation of existing hospitalization, and

*A hospitalization is defined as an inpatient overnight stay, but this can be shorter than 24 hours.*

- is another medically significant event defined as an event that may not be immediately life-threatening or result in death or hospitalization but may jeopardize the patient or may require intervention to prevent any of the above listed outcomes.

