#### 8.1.2.1 Excluded events

Hospitalization for the following reasons will not be regarded as serious (i.e. will not be immediately reportable):

- routine treatment or monitoring of the disease under study, including hospitalization due to trial-related procedures, not associated with any deterioration of the patient’s status,

- elective or pre-planned treatment (before signing the ICF) for a pre-existing condition that is unrelated to the disease under study and has not worsened since signing the ICF,
- treatment on an emergency outpatient basis for an event not fulfilling any of the definitions for an SAE and not resulting in hospital admission,
- underlying disease progression (the adrenal malignancy which is the basis for the patient enrollment in the trial) and events which are unequivocally (without doubt) related to the disease progression, and
- social reasons, respite care, and in the absence of a medical condition.

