## 8.5 Reporting by the investigational site

### 8.5.1 Adverse events

Any AE (including SAEs), whether, or not considered to be causally related to the trial medication and regardless of its seriousness, must be reported (described and recorded) in the AE section of the patient's eCRF on an ongoing basis.

A pre-existing condition is a clinical condition (including a condition being treated) that is diagnosed before the patient signs the ICF and that is documented as part of the patient's medical history; any clinically significant worsening of a pre-existing condition constitutes an AE. Also, any recurrence of a pre-existing condition is an AE.

The questions concerning whether the condition existed before the start of the active phase of the study and whether it has increased in severity and/or frequency will be used to determine whether an event is a TEAE. An AE is considered to be treatment-emergent if it is not present when the active phase of the study begins and is not a chronic condition that is part of the patient's medical history, or it is present at the start of the active phase of the study or as part of the patient's medical history, but the severity or frequency increases during the active phase. The active phase of the study begins at the time of the first dose of the study drug. The active phase of the study ends 100 days after the last study drug administration [REDACTED]

A standardized question such as "Have you had any health problems since your last visit or since you were last questioned?" will be given by the Investigator or the investigational site personnel at each contact with the patient.

[figure not shown]
Progression of the underlying disease or an AE unequivocally (without doubt) related to the progression of the underlying disease, regardless of its outcome or seriousness criteria, does not need to be reported as an AE/SAE. However, the medical conditions and underlying diseases associated with disease progression needs to be captured on the AE eCRF page (as a non-serious AE). An SAE must be reported only if there are clinical symptoms/signs that cannot be without doubt associated with the progression of the underlying disease.

Whenever possible, a diagnosis rather than symptoms should be provided (e.g. anemia instead of low Hb).

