### ***8.5.2 Documenting in the eCRF***

The reported term should be a medical diagnosis or sign/symptom of the event, not a procedure. Each symptom in a constellation of symptoms should be listed separately if the Investigator has not made a preliminary/tentative summary diagnosis.

Fluctuations or re-occurrences of a condition, which are considered normal for the patient and are recorded in patient's eCRF medical history, do not need to be reported as an AE. However, if the condition deteriorates during the trial it needs to be captured as an AE.

If the same AE occurs repeatedly it must be assessed and documented separately each time, if there are "AE-free" time periods between the AEs.

If possible, each AE should be evaluated to determine:

- event term or a description of the AE in medical terms (not as reported by the patient),
- severity grade as assessed by the Investigator (1 - 5 per NCI CTCAE v5.0),
- its causal relationship to study treatment as assessed by the Investigator (suspected; not suspected),
- event duration, including onset date and end date,
- action taken with study treatments due to the reported event (no action taken; interruption of administrations; treatment permanently withdrawn; other),
- other action taken (no action taken; medication required; surgical intervention required; other),
- event seriousness (non-serious or serious AE),
- event outcome (resolved without sequelae, resolved with sequelae, not resolved, fatal, unknown), and
- disease progression-related event (yes, no).

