  - a) Missing day - Impute the 1st of the month unless month is same as month of first dose of study drug then impute first dose date,
  - b) Missing day and month – impute 1st January unless year is the same as first dose date then impute first dose date. If this rule leads to an imputed start date posterior to the end date (after imputation of end date if needed), then impute 1st January for start date rather than first dose date,
  - c) Completely missing – impute first dose date unless the end date suggests it could have started prior to this in which case impute the 1st January of the same year as the end date.
- Partial or missing AE end dates will be imputed as follows:
  - a) Missing day - impute the last day of the month. If the patient died in the same month, then set the imputed date as the death date,
  - b) Missing day and month – impute 31st December. If the patient died in the same year, then set the imputed date as the death date,
  - c) Completely Missing – No imputation.

If a patient is known to have died where only a partial death date is available, then the date of death will be imputed as the latest of the last date known to be alive +1 from the database and the death date using the available information provided:

- a) For Missing day only – using the 1st of the month,
- b) For Missing day and Month – using the 1st of January.

All AE classified as **not** TEAE via programming will be reviewed and confirmed during the DRM meeting.

In case of worsening of an AE, the worst grade (NCI CTCAE v5.0) will be used for the analysis and will be counted as one AE.

An overview table presenting number and percentage of patients and the number of AEs in the following categories will be created for the SAF, by cohort:

- Any AE
- Any TEAE

- Any local administration site conditions at a site of EO2401 local administration (LASR)
- Any TEAE with worst grade 1 (NCI CTCAE v5.0)
- Any TEAE with worst grade 2 (NCI CTCAE v5.0)
- Any TEAE with worst grade 3 (NCI CTCAE v5.0)
- Any TEAE with worst grade 4 (NCI CTCAE v5.0)
- Any TEAE with worst grade  $\geq 3$  (NCI CTCAE v5.0)
- Any TEAE leading to death
- Any disease progression-related TEAE
- Any TEAE related to study treatment
- Any TEAE related to study treatment with worst grade  $\geq 3$  (NCI CTCAE v5.0)
- Any TEAE leading to definitive discontinuation of any study drug
- Any TEAE leading to definitive discontinuation of EO2401
- Any TEAE leading to definitive discontinuation of nivolumab

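### Protocol 8.5.1 has progression-associated conditions entered as non-serious, against the SAE definition in 8.1.2, so events that meet that definition leave the SAE counts of the phase 1 primary endpoint

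*Protocol*

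**What the plan says.** Protocol 8.1.2 defines seriousness by outcome: "An SAE is any untoward medical occurrence that at any dose fulfills one or more of the following criteria". The criteria that follow include death, immediate threat to life, persistent disability and inpatient hospitalization.

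Protocol 8.1.2.1 then lists exclusions. Its lead-in reads "Hospitalization for the following reasons will not be regarded as serious", and it explains this as meaning that the events are not immediately reportable. One item on the list is progression of the adrenal malignancy and events unequivocally related to it.

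Protocol 8.5.1 opens with a general duty: "Any AE (including SAEs), whether, or not considered to be causally related to the trial medication and regardless of its seriousness, must be reported". Later in the section, progression, or an AE unequivocally related to it, "regardless of its outcome or seriousness criteria, does not need to be reported as an AE/SAE". The next sentence requires that the conditions associated with progression still go on the AE page, each as a non-serious AE ("needs to be captured on the AE eCRF page (as a non-serious AE"). The paragraph closes with a limit: "An SAE must be reported only if there are clinical symptoms/signs that cannot be without doubt associated with the progression".

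Protocol 8.5.2 lists the AE fields. They include grade, outcome (with fatal as an option), seriousness, and "disease progression-related event (yes, no".

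SAP 7.11.2 has overview rows for serious TEAEs, grade 3 or higher TEAEs, progression-related TEAEs, and "Any TEAE leading to death". It tabulates serious and non-serious TEAEs separately by system organ class and preferred term.

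**The concern.** Exempting progression from expedited SAE reporting is common and defensible. Entering a seriousness value that the protocol's own definition contradicts is a different matter, because that value is the one the tables use.

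SAEs are named in the phase 1 primary endpoint (Protocol 3.2.1). SAE incidence against the concurrent controls is a secondary endpoint of the randomized extension (Protocol 3.2.2). If events that meet the definition are coded non-serious, both are understated by an amount that depends on the investigator's attribution in an open-label trial. Attribution is not always easy here: Protocol 4.4 expects response patterns that may resemble tumor flare, and Protocol 1.3.5 accepts that expanded T cells might attack normal tissue.

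**Working it through.** No formula applies, and the plan states no figure to reproduce. The check follows one on-treatment event through the sections. In the first three rows the investigator regards the event as certainly due to progression.

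| Event | 8.1.2 | 8.1.2.1 | 8.5.1 | Result in SAP 7.11.2 |
|---|---|---|---|---|
| Non-fatal, hospitalised | Serious | Excluded | Non-serious | Non-serious table; progression-related row |
| Non-fatal, life-threatening or disabling | Serious | Not covered | Non-serious | Non-serious table; progression-related row |
| Fatal | Serious | Not covered | Non-serious | Non-serious table and leading-to-death row; progression-related row |
| Link to progression in doubt | Serious | Not excluded | SAE | Serious table |

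What follows:

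1. For hospitalization alone, 8.1.2.1 and 8.5.1 agree with each other and both depart from 8.1.2. The departure is declared, although 8.1.2.1 ties it to immediate reporting rather than to how the event is stored.
2. For death, threat to life and disability, 8.5.1 stands alone. Nothing in 8.1.2.1 supports widening the exclusion to every outcome and criterion.
3. Section 8.5.1 also conflicts with its own opening duty to record every AE and SAE. It conflicts as well with Protocol 7.3, where illnesses that first occur or worsen on study are documented as SAEs if they meet a seriousness criterion.
4. The two sentences in 8.5.1 differ in scope. The reporting exemption requires an unequivocal link, while the sentence that sets non-serious coding speaks only of association with progression.
5. No visible SAP rule restores seriousness for events that carry the progression flag. A fatal TEAE can therefore count as leading to death and also sit in the non-serious table.
6. Some of the loss can be recovered from the AE record. Fatal outcome and grade are kept. None of the AE fields listed in 8.5.2 records hospitalization, so for a non-fatal event entered as non-serious that fact may not be retrievable without a query.

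**The case against.** The strongest reply is that the exemption is narrow and the events stay visible. Much of this stands.

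- **Scope.** The exemption needs a link to progression beyond doubt. A possible treatment-induced flare is doubtful by nature and stays an SAE. If it is coded otherwise, that is misattribution, which the rule does not ask for.
- **Deaths.** A reader might infer that deaths are understated too. The documents do not support that. Deaths are a separate component of the phase 1 endpoint. Protocol 8.5.1 puts date and causes on a dedicated eCRF page, and SAP 7.8.7 reports the number of OS events, which are deaths from any cause. A missing table of deaths by cause cannot be asserted either, because the full table list is in SAP appendices that are not available.
- **Omitted records.** A reader might infer that sites may leave these events out altogether. The sentence that follows the exemption requires the associated condition on the AE page, so the natural reading is no SAE report but a recorded AE.
- **Size.** A reader might try to size the loss from the protocol's literature figures. Assume exponential survival, treatment until median PFS, and a 100-day window (100/30.5 = 3.28 months) in the 52 ACC patients (26 + 7 + 19). The anti-PD-L1 trial (median PFS 2.6, median OS 10.6 months) gives 1 − exp(−(ln 2/10.6) × 5.88) = 0.32, about 17 deaths. The anti-PD-1 trial (2.1 and 24.9 months) gives 1 − exp(−(ln 2/24.9) × 5.38) = 0.14, about 7. With a 30-day window the same method gives about 11 and 4. None of these measures the problem. They count deaths, which are captured elsewhere, and the documents do not say what share would be attributed to progression.
- **Decision impact.** The phase 1 endpoint is a descriptive medical assessment with no visible SAE threshold. The randomized groups have 13, 2 and 4 patients, and no direct statistical comparison is planned.

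The reply does not remove the contradiction between 8.1.2 and 8.5.1, or the wrong value in the seriousness field.

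**Conclusion.** The plan is wrong as written on this point. Protocol 8.5.1 instructs sites to store as non-serious some events that 8.1.2 defines as serious, and it goes beyond the hospitalization-only exclusion in 8.1.2.1. Such events leave the serious TEAE counts, and a fatal one can be shown as non-serious.

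The effect is confined to the SAE counts. It falls mainly on non-fatal hospitalised or life-threatening events. Severe and fatal events remain visible through grade, outcome and the progression flag.

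The size of the undercount cannot be derived from the documents, and no number should be attached to it. The conclusion assumes that sites follow 8.5.1 as worded and that no redacted text or SAP appendix contains a rule restoring seriousness. The point deserves correction because it touches a named component of the primary endpoint, but it does not threaten the trial's conclusions on survival or all-cause death.

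**What to change.** **Protocol.** Reconcile 8.1.2, 8.1.2.1 and 8.5.1. Every event on the AE page should carry its true seriousness and outcome under 8.1.2, together with the existing progression flag. Limit the exemption for unequivocally progression-related events to expedited 24-hour reporting, and add a matching carve-out in 8.5.3, which otherwise requires 24-hour notification of every SAE.

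**SAP 7.11.2.** Show serious TEAEs and TEAEs leading to death twice: including and excluding events flagged as progression-related.

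**Existing records.** Query flagged events already entered as non-serious, to establish whether a seriousness criterion was met. If that is not feasible, at least tabulate them by grade and outcome, and state in the study report that hospitalization could not be recovered.

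**Cost.** Protocol wording, queries on records already entered, and a few extra table rows. No new patient procedures are needed. The reported SAE rate will rise somewhat; the split presentation lets the reader see how much of that is attributed to progression.

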### ***8.5.2 Documenting in the eCRF***

The reported term should be a medical diagnosis or sign/symptom of the event, not a procedure. Each symptom in a constellation of symptoms should be listed separately if the Investigator has not made a preliminary/tentative summary diagnosis.

Fluctuations or re-occurrences of a condition, which are considered normal for the patient and are recorded in patient's eCRF medical history, do not need to be reported as an AE. However, if the condition deteriorates during the trial it needs to be captured as an AE.

If the same AE occurs repeatedly it must be assessed and documented separately each time, if there are "AE-free" time periods between the AEs.

If possible, each AE should be evaluated to determine:

- event term or a description of the AE in medical terms (not as reported by the patient),
- severity grade as assessed by the Investigator (1 - 5 per NCI CTCAE v5.0),
- its causal relationship to study treatment as assessed by the Investigator (suspected; not suspected),
- event duration, including onset date and end date,
- action taken with study treatments due to the reported event (no action taken; interruption of administrations; treatment permanently withdrawn; other),
- other action taken (no action taken; medication required; surgical intervention required; other),
- event seriousness (non-serious or serious AE),
- event outcome (resolved without sequelae, resolved with sequelae, not resolved, fatal, unknown), and
- disease progression-related event (yes, no).

### ***8.5.3 Immediately reportable events - Serious Adverse Events***

The Investigator or designated investigational site staff must immediately (within 24 hours) notify/report to pharmacovigilance at the Sponsor.

Any initial or medically relevant follow-up information about SAEs, or pregnancies (see [Section 8.2](#)).

All immediate reports from the investigational site to the Safety Group (i.e. SAEs and pregnancy reports) must also be recorded in the site's source documentation.

The primary mode of reporting a SAE is based on entering the appropriate and complete information into the clinical database via the SAE reporting form and submitting the SAE form [REDACTED] to the trial Safety Group within 24 hours of obtaining knowledge of the event.

The SAE Form [REDACTED] is to collect data surrounding the event (e.g. the nature of the symptom[s], time of onset in relation to initiation of therapy, duration, intensity, and whether, or not therapy was interrupted or discontinued). The Investigator's assessment of the probable cause of the event will also be included. In addition, relevant medical history, concomitant medications, laboratory and diagnostic test reports, and procedures as well as all pertinent medical information related to the event will also be collected. Once the AE page has been updated in the eCRF for an SAE by the site, the site will submit it to the safety group within the system. Then an alert from the clinical database will be initiated and sent to the Safety Group. The Safety Group will generate the SAE report, a PDF extracted from the clinical database, and send to the Sponsor.

The Safety Group will generate SAE queries requesting missing information, correction of implausible, etc., and add the queries directly in the clinical database. It is the Investigator's responsibility to be diligent in providing the answer as soon as it is available by entry of the corrections in the eCRF and submission of the follow-up SAE report to the Safety Group.

In case of technical or any other reason the SAE reporting cannot be carried out via the EDC system per above, the Investigator (or designated investigational site staff) will complete a paper SAE form and send to the Safety Group as outlined below. The paper SAE form will be provided to the sites prior to start of the study.

[REDACTED]

When a paper form is completed, follow-up information should not be reported on the same form that was used for the initial reporting, but using a new form filled in only with the new information. Changes/completions need to be done in a Good Clinical Practice (GCP)-compliant manner (i.e. dated and initialized). Originals of the report forms must be kept in the site study file.

Initial reports of SAEs should never be left on telephone voicemails. In case of using the paper SAE form, please always fax or e-mail the SAE report, and follow-up with a telephone call if needed.

#### *8.5.3.1 Minimum notification/reporting requirements*

The following information must be provided for a valid notification/report:

- identification of the notifying/reporting person (e.g. name of the reporter),
- identification of the patient (e.g. patient trial identification number),
- concerned IMP and/or clinical trial (e.g. EO2401, trial EOADR1-19),
- reason for notification/reporting (i.e. SAE, or pregnancy), and
- event term.

*In addition, providing the **assessment of the causal relationship** is necessary for comprehensive evaluation by the Sponsor.*

[figure not shown]

## **8.6 Independent Data Monitoring Committee (IDMC)**

The IDMC will serve as an external monitoring group for the study. The primary role of the IDMC will be to examine the safety and tolerability of study participants throughout the duration of the study. The IDMC will be created to further protect the rights, safety, and well-being of patients who will be participating in the trial by monitoring their progress and results. The IDMC will examine the safety data of Cohort 1, including possible transitions between sub-cohorts (1a, 1b, 1c, and 1d) and provide advice and guidance in relation to the recruitment start of Cohort 2A/B and Cohort 3A/B.

The major tasks for the IDMC are outlined in relation to the description of the design of the trial (see [Section 4.2](#)).

A large black rectangular box used to redact sensitive information.

The frequency of IDMC meetings will be based on the development of the safety profile of the study treatments and necessity to assess safety events and progression steps in the trial (e.g. transitions between cohorts).

In addition, in relation to the randomized extension of Cohort 2A, the IDMC will oversee and validate the interim first stage analysis of the Simon's two-stage design as performed by the Sponsor (or designee); see [Section 9.4.2](#).

The IDMC members are to be international oncology/immune-oncology experts who are not in other ways than via the IDMC involved in the current trial. The IDMC will be described in detail in an IDMC Charter.

